In an event that one Attain Stability Quad MRI SureScan LV Lead (Model 4798) is determined to be not suitable for a patient after the initial lead insertion; the implanting physician must assess the onset of any potential AEs. A second Attain Stability Quad MRI SureScan LV Lead (Model 4798) may only be introduced upon confirmation that no system-related AEs resulted from the first Attain Stability Quad MRI SureScan LV Lead (Model 4798) implant attempt. Any LV lead related AE observed during the initial LV lead attempt prohibits an attempt of a second Attain Stability Quad MRI SureScan LV Lead (Model 4798).

If the subject does not have a successful Attain Stability Quad MRI SureScan LV Lead (Model 4798) implant at the conclusion of the initial implant procedure, the subject should be followed until procedure or system related AEs are resolved or are unresolved with no further actions planned, whichever occurs later.

If an attempt to implant the Attain Stability Quad MRI SureScan LV Lead (Model 4798) does not occur, or if the Model 4798 LV lead cannot be implanted, the reasons why the lead was not attempted or attempted but not implanted must be documented on the Implant and Study Exit CRF. See additional definitions below.

No Attain Stability Quad MRI SureScan LV Lead (Model 4798) Attempted (lead not inserted into the body)

An Attain Stability Quad MRI SureScan LV Lead (Model 4798) attempt is defined as any time a Model 4798 lead is introduced into the body. Subjects that do not have an Attain Stability Quad MRI SureScan LV Lead (Model 4798) implant attempted will be exited from the study following their implant procedure

unless another Attain Stability Quad MRI SureScan LV Lead (Model 4798) attempt is scheduled. Adverse events, device deficiencies and deviations must be documented before the subject is exited.

Attain Stability Quad MRI SureScan LV Lead (Model 4798) Attempted but Not Implanted

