15.14. System Modifications

A system modification will be reported in the event the device and/or leads require invasive modification (e.g. generator or lead explant, generator or lead replacement, lead repositioning, etc.). In the event of a system modification, regardless of outcome of the modification, subjects should remain in the study

when possible and the follow-up visit schedule for the subject will remain unchanged. For a system modification the following information/activities are required to be collected:

- Modification or replace/explant date
- Reason for modification
- Information on device or lead modified
- Information on any replacement device(s)
- Final device interrogation/save-to-media
- Study deviations
- AEs and device deficiencies (as applicable)

It is recommended that all explanted Medtronic products (device, leads, etc.) are returned to Medtronic for analysis per local process and when permissible by local laws and regulations.

In the event that subject has a re-attempt after a previous unsuccessful system modification, the subsequent attempt(s) must be reported via CRF as separate system modifications.

Attain Stability Quad MRI SureScan LV Lead (Model 4798) repositioned or replaced with another Attain Stability Quad MRI SureScan LV Lead (Model 4798)

If the Attain Stability Quad MRI SureScan LV Lead (Model 4798) is repositioned or replaced, the following LV lead electrical tests and data collection must be completed:

Lead Impedance

- Obtain LV Lead Impedance Test for the final programmed vector
- Perform a manual test for a missing value
- NOTE: Retain printouts at the site

Pacing Capture Thresholds (PCT)

- Obtain a PCT at 0.5ms pulse width using Vector Express on the final programmed vector
- Perform a manual test for a missing value
- NOTE: A onetime manual reprogramming the pulse width to 0.5ms will be required (Out of the box pulse width is set at 0.4ms)
- NOTE: Retain printouts at the site

Phrenic Nerve Stimulation (PNS)

- Test for presence of PNS at 8.0V at 0.5ms on final programmed vector
- NOTE: If PNS is present at 8.0V at 0.5ms, measure the PNS threshold at 0.5ms
- NOTE: PNS observed during this testing will not be considered an AE

Other Data Collection

- Record the reason why the final configuration was selected for final programming
- Record any programming changes to the LV lead apart from the LV lead pacing vector since the last visit and provide rationale for the change(s)

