Attain Stability Quad MRI SureScan LV Lead (Model 4798) capped or explanted without replacement with another Attain Stability Quad MRI SureScan LV Lead (Model 4798)

If the Attain Stability Quad MRI SureScan LV Lead (Model 4798) is capped or explanted without replacement while the subject is in the study, subjects will continue to be followed per their original follow-up schedule for safety monitoring until study closure. LV lead electrical testing and interrogation files will not be required at follow-ups for subjects without the full protocol required system implanted.

Explant of the Attain Stability Quad MRI SureScan LV Lead (Model 4798) and the Medtronic CRT-P or CRT-D device without replacement with another Attain Stability Quad MRI SureScan LV Lead (Model 4798) and Medtronic CRT-P or CRT-D device

Subjects who have their Attain Stability Quad MRI SureScan LV Lead (Model 4798) and Medtronic CRT-P or CRT-D device explanted without replacement during a system modification procedure should be exited from the study as soon as all system related and/or system modification procedure related AEs are resolved. If no system or procedure related AEs are present at the conclusion of such a system modification procedure, the subject should be exited immediately.

Medtronic CRT-P or CRT-D device explanted without replacement, Attain Stability Quad MRI SureScan LV Lead (Model 4798) remains implanted

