15.16.2. Investigator Withdraws Subject

No subjects should be withdrawn by investigators unless compelling medical justification is present. It is recommended investigators discuss any withdrawals with the study sponsor prior to exiting subjects. If

an Investigator withdrawal is necessary, the following data should be collected prior to subject withdrawal if possible:

- Report the reason for subject withdrawal
- Final device interrogation/save-to-media
- Study deviations
- AEs and device deficiencies (as applicable)

The following are reasons for investigator-initiated subject withdrawal;

Medical Necessity

A subject may be exited from the study if an investigator feels it is necessary to withdraw the subject from the study due to a medical condition or other reason. In such cases, the subject will be notified and provided an explanation regarding the reasons for the study exit.

Explant of Medtronic CRT-P or CRT-D Device and Attain Stability Quad MRI SureScan LV Lead (Model 4798)

Subjects in which the Attain Stability Quad MRI SureScan LV Lead (Model 4798) and the Medtronic CRT-P or CRT-D device are explanted without replacement (i.e., subject no longer has a Medtronic CRT-P or CRT-D device and an Attain Stability Quad MRI SureScan LV Lead (Model 4798) implanted) shall be exited from the study (refer to Section 15.8.2.2). Subjects exposed to an Attain Stability Quad MRI SureScan LV Lead (Model 4798) through a lead attempt must be followed through at least one month or until all implant related AEs (system-, and/or procedure-related) have resolved or are unresolved with no further actions planned. Subjects who have either an Attain Stability Quad MRI SureScan LV Lead (Model 4798) (active or not active) or a Medtronic CRT-P or CRT-D device implanted will continued to be followed for safety until study completion.

Attain Stability Quad MRI SureScan LV Lead (Model 4798) Not Implanted

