Subjects that are not anticipated to have an implant attempt (e.g. do not meet inclusion/exclusion criteria) must be exited from the study. Subjects that have a CRT system implant attempt, but who do not have an Attain Stability Quad MRI SureScan LV Lead (Model 4798) attempted (See Section 15.8.2.2 for definition) will be exited from the study following their procedure unless an Attain Stability Quad MRI SureScan LV Lead (Model 4798) attempt is scheduled. If this attempt is more than 30 days from the baseline assessment, verification of the baseline data must be completed prior to a subsequent implant attempt.

Subjects with an unsuccessful Attain Stability Quad MRI SureScan LV Lead (Model 4798) implant attempt will be followed at pre hospital discharge and one month unless there are ongoing implant related AEs (system- and/or procedure related), in which case they will be followed beyond one month until the implant related (i.e., system, and/or procedure related) AEs have been resolved or are considered unresolved with no further actions planned. The subjects may be followed via a clinic visit or by phone contact. In geographies where the Attain Stability Quad MRI SureScan LV Lead (Model 4798) is market-released, subjects will be exited from the study after the assessment of implant procedure or CRT system related AEs if the initial attempt of one Attain Stability Quad MRI SureScan LV Lead (Model 4798) model was unsuccessful. The subject may undergo implant attempts with any market released LV lead that provides the best benefit to the patient, but data collection on these subsequent attempts will not be required as these subjects will be considered exited from the study.

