17.1.3. Event Updates and Resolution

For any changes in status of a previously reported AE (i.e. change in actions taken, change in outcome, change in relatedness), information needs to be updated on, or added to the original AE form. All AEs must be followed until the AE has been resolved, is unresolved with no further actions planned, the subject dies or exits the study, or until study closure, whichever occurs first.

In the event that a subject is exited from the study prior to their 6 month visit, all efforts should be made to continue following the subject until all unresolved system or procedure related adverse events, as classified by the investigator, are resolved or unresolved with no further actions planned.

At the time of study exit, all collected AEs with an outcome of "Unresolved" must be reviewed and an update to the original AE must be reported. At a minimum, if there are no changes to the description, relatedness, test and procedures or actions taken, the outcome must be updated to reflect "Unresolved at time of study exit".

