17.2. Definitions/Classifications

Where the definition indicates “device”, it refers to any device used in the study. This might be the device under investigation, or any market released component of the system, and includes but is not restricted to: the CRT-P or CRT-D device, the RA, RV or LV leads, the programmer, and implant tools.

Table 12: Adverse Event and Device Deficiency Definitions

General	
Adverse Event (AE)	
Any untoward medical occurrence, unintended disease or injury, or untoward clinical signs (including abnormal laboratory findings) in subjects, users or other persons, whether or not related to the investigational medical device
 
NOTE 1: This definition includes events related to the investigational medical device or the comparator. NOTE 2: This definition includes events related to the procedures involved. NOTE 3: For users or other persons, this definition is restricted to events related to investigational medical devices. (ISO 14155:2011, 3.2)

Adverse Device Effect (ADE)	
Adverse event related to the use of an investigational medical device
 
NOTE 1: This definition includes adverse events resulting from insufficient or inadequate instructions for use, deployment, implantation, installation, or operation, or any malfunction of the investigational medical device. NOTE 2: This definition includes any event resulting from an error use or from intentional misuse of the investigational medical device. (ISO 14155:2011, 3.1)

Device Deficiency (DD)	
Inadequacy of a medical device with respect to its identity, quality, durability, reliability, safety or performance.
 
NOTE: Device deficiencies include malfunctions, use errors and inadequate labeling (ISO 14155:2011, 3.15)

Relatedness	
Procedure Related	
An Adverse Event that is directly related to the implantation or surgical modification of the system.
 
NOTE: In general, this excludes events that are inherent to any surgical procedure (e.g. anesthesia complications) as well as indirect subsequent consequences of the procedure (e.g. reaction to pain medication).

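### After explant of both lead and device without replacement, Sections 15.14 and 15.16.2 give different study-exit rules, and the Section 15.14 rule leaves later adverse events of the explant with no planned capture.

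*Protocol*

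**What the plan says.** Section 15.14 of the Protocol treats explant of both the Model 4798 lead and the CRT device without replacement as a separate case. Subjects leave the study once all system related or modification-procedure related events are resolved, and "If no system or procedure related AEs are present at the conclusion of such a system modification procedure, the subject should be exited immediately".

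Section 15.16.2 has a paragraph headed for the same case. It says these subjects shall be exited, and then that subjects exposed to the lead "through a lead attempt must be followed through at least one month or until all implant related AEs" have resolved or remain open with nothing further planned. Section 15.8.2.2 makes exposure broad: an "attempt is defined as any time a Model 4798 lead is introduced into the body".

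Neighbouring cases are followed for longer:

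- After a system modification in general, Section 15.14 keeps subjects in the study when possible and says that "the follow-up visit schedule for the subject will remain unchanged".
- If the lead alone is capped or explanted, "subjects will continue to be followed per their original follow-up schedule for safety monitoring until study closure".
- After an unsuccessful implant attempt, Section 15.16.2 says subjects "will be followed at pre hospital discharge and one month unless there are ongoing implant related AEs", in which case follow-up is longer. A clinic visit or phone contact is allowed.

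Table 12 in Section 17.2 defines a procedure related event as "An Adverse Event that is directly related to the implantation or surgical modification of the system" and has a separate fixation-related (side-helix) category under LV lead-related events. Section 17.1.3 follows events until they close, or "the subject dies or exits the study, or until study closure, whichever occurs first".

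**The concern.** A site that explants the whole system and sees no related event at the end of the procedure has two instructions for the same subject. One says exit now. The other sets a period of at least one month, with an unclear start and an alternative joined by an or.

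Under the Section 15.14 wording, the subject has left before any delayed effect of the explant could show itself. The Protocol's definitions make such an effect a reportable procedure related event, and a fixation-related one if the side helix caused it. The study therefore intends to collect these events but stops observing the subject first. At stake are the completeness of adverse event reporting after full-system explant and, if such an event were a fixation-related complication, the fixation group of secondary objective #2.

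**Working it through.** The point rests on comparing rules, not on a figure in the plan.

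**Step 1. Do the two sections cover the same subjects?** Both concern explant of lead and device without replacement. The one-month clause refers to subjects exposed through a lead attempt. Since an attempt is any introduction of the lead into the body, every subject with an implanted and later explanted lead meets that condition.

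**Step 2. Compare minimum follow-up when no related event is present.**

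| Situation | Minimum follow-up | Source |
|---|---|---|
| Lead and device explanted, no event at end of procedure | 0 days | 15.14 |
| Same situation | At least one month, or until implant related events close; start not stated | 15.16.2 |
| Unsuccessful attempt, no event | Pre-hospital discharge and one month | 15.16.2 |
| Lead alone capped or explanted | To study closure | 15.14 |

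**Step 3. Compare the closure rule for open events.** Section 15.14 requires resolution. Section 15.16.2 also accepts an unresolved event with nothing further planned.

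**Step 4. Is a new event caught after exit?** Section 15.15 requires no study visits after exit. For exits before the 6-month visit, Section 17.1.3 asks sites to make every effort to keep following events that are still unresolved. That covers events already open, not events that start later. An event first appearing after an event-free explant has no planned route into the data.

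**Step 5. Could this change the primary safety decision?** Section 19.1.1 counts only the first lead-related complication and censors event-free subjects at last known exposure to the lead. A subject explanted because of a lead complication is already an event. One explanted for another reason is, on the natural reading, censored at removal.

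As a bounding check, suppose missed events did count. Assume 400 subjects, no censoring and 16 events (96.0%, the Model 4298 rate in Table 16). With d events in n subjects, S = 1 − d/n, v = d/[n(n − d)], se = √v / |ln S|, and the lower bound is S^exp(1.96 × se).

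- d = 16: S = 0.960; v = 16/(400 × 384) = 0.000104; se = 0.0102/0.0408 = 0.250; bound = 0.960^1.632 = 0.9355.
- Adding 1, 2, 4 or 10 missed events gives 0.9325, 0.9295, 0.9236 or 0.9060.
- The bound stays above 0.87 up to 38 events (0.8718) and falls below it at 39 (0.8690).

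**The case against.** The strongest reply is that Section 15.16.2 does not plainly contradict Section 15.14. It too says these subjects shall be exited. Its one-month clause speaks of implant related events and is joined by an or, so on a literal reading a subject with no event could leave at once. If the month runs from the attempt, the conflict affects only explants in the first month after implant. This stands in part: the text does not establish a month counted from explant. It does not remove the problem, because the start is nowhere stated and sites cannot settle it themselves. The rule for unsuccessful attempts, which names a one-month contact even without events, favours reading one month as a minimum. That rule is itself qualified: in market-released geographies those subjects exit after the event assessment, with no time given.

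A reader might also draw four stronger inferences that the documents do not support:

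- **A count of affected subjects from implant-site infection in Table 24 (44 of 3,246).** A subject explanted for infection would normally have a related event open at the end of the procedure, so Section 15.14 keeps that subject in until it resolves. The infection rate neither estimates nor bounds the group that exits immediately.
- **Loss of all safety data after removal.** Subjects with an open event stay in, and subjects whose lead alone is explanted are followed to study closure.
- **Removal as the point where the helix does its harm.** The Protocol does not say so.
- **A material effect on the 6-month complication-free rate.** First-event counting and censoring at last exposure largely remove it.

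**Conclusion.** The two sections give different exit rules for the same situation, and the Section 15.14 rule leaves related events that first appear after an event-free full explant without planned capture. The sections also disagree on when an open event is closed.

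The size cannot be computed. The Protocol gives no rate of full-system explant and no share of explants that are event-free at the end of the procedure; the number is probably very small. The consequence is for completeness of adverse event data, and possibly for the fixation-related data of secondary objective #2. The 87% criterion is not threatened: under the stated assumptions (400 subjects, 16 events, no censoring), ten further events still leave the lower bound at 0.9060.

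This should be corrected because the instructions conflict and the correction is cheap, not because a primary conclusion depends on it.

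**What to change.** Reconcile the explant paragraph of Section 15.14 with the explant and unsuccessful-attempt paragraphs of Section 15.16.2, so that one adverse event follow-up rule applies before study exit after explant of lead and device.

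- State the event from which the one-month period runs. To capture events of the explant itself, the period has to cover that procedure.
- Say how the contact is made. The phone contact already allowed after an unsuccessful attempt would suffice.
- Use one wording for closing an open event in both sections.

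This concerns safety data collection and study exit only. It proposes no rule on explant or on care afterwards, and the sponsor decides the final wording. The cost is a few sentences of Protocol text and one contact for each affected subject, probably a handful at most.

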15.15. Study Exit

Study Exit is defined as the moment when a subject officially stops participating in the study. Date and reason for subject exit must be reported to Medtronic at the earliest opportunity.

Subjects will be exited from the study for any of the following situations:

- Study completed
- Subject lost to follow-up
- Subject did not meet eligibility criteria and was not yet implanted with an Attain Stability Quad MRI SureScan LV Lead (Model 4798)
- Subject did not have a successful implant and no attempt at re-implant is made
- Subject did not provide consent or data protection authorization, as required by law
- Subject chooses to exit (i.e. revokes consent)
- Investigator withdraws subject

Prior to exiting a subject from the study, it is recommended to follow the subject until all ongoing system- and procedure-related AEs are resolved, unresolved with no further actions planned, or 30 days post the 6 month visit, whichever occurs first. Following exit, subjects will continue to receive standard medical care. There will be no further required study-related follow-up visits for these subjects. All data through the time of the subject's exit will be available for data analyses.

If possible, the following procedures should be performed / data collected at the exit visit:

- Report the reason for exit
- Final interrogation file (or CareLink transmission) for exits occurring prior to the 6 month visit
- Study deviations
- AEs and device deficiencies (as applicable)

After subjects are exited from the study they should receive standard medical care and should be managed and followed per physician discretion.

15.15.1. Study Completed

All subjects will be followed until FDA Pre-Market Approval (PMA) of the Attain Stability Quad MRI SureScan LV Lead (Model 4798). Medtronic will notify sites when the study is complete. Upon exiting subjects, if the current follow-up visit and exit visit are combined, then both the follow-up CRF and a Study Exit CRF need to be completed but only one device interrogation/save-to-media needs to be completed and collected. If AEs are unresolved at time of exit, it should be noted on the AE CRF that the AE is unresolved at time of study exit.

15.15.2. Lost to Follow-up

In the case that the subject is determined to be lost to follow-up, details of a minimum of two attempts and the method of attempt (e.g., one letter and one phone record or two letters) to contact the subject must be recorded. In addition, follow the regulations set forth by the governing IRB or EC.

